##### 5.4.2.3. Subgroup and Covariate-adjusted Analyses

Subgroup and covariate-adjusted analyses will be performed. These subgroups/covariates may include PrEP use (based on the different PrEP use data sources), baseline Ad26 seropositivity status and titers, presence of risk factors for HIV infection, and other baseline demographic factors (age strata/region/country).

If there is substantial PrEP use detected over the course of the study (eg prevalence at any time above 20%), then a Cox model with PrEP detectability as a time-varying covariate may be used to assess different vaccine efficacy by time-varying subgroup and for each subgroup separately. More specifically, the primary analysis may be repeated where only mITT infection endpoints with no evidence of PrEP use at the time of HIV-1 diagnosis and at the time of the earliest evidence of infection will be included in the analysis. FTC/TDF concentrations (see Section 3.6.1) will be used to determine eligibility for this analysis. A participant is eligible if their concentration is below the lower limit of detection as defined above at the diagnosis visit and at the visit with earliest evidence of HIV-1 infection (if different from the diagnosis visit). Since the ARVs are only detectable in plasma for roughly 14 days after a single dose (Patterson et al. 2011) and some participants may have become infected before the 14-day window, with this approach we are not assured that all those included in the analysis were not using prophylactic ARVs at the time of infection. Therefore an additional analysis may be conducted that addresses this issue by also excluding participants

from the HIV-1 acquisition analysis if they self-report ARV use in the last 30 days at either the diagnosis visit or the last visit prior to diagnosis.

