participation in the study as, due to the high effectiveness of PrEP, these individuals are not considered to be at increased risk of HIV acquisition. However, once enrolled in the study and having received their first vaccination, a participant who changes his/her mind regarding PrEP use is permitted to take PrEP according to the site PrEP plan and will continue to receive further vaccinations. In case of PrEP use during the study, safety monitoring for PrEP will be the responsibility of the prescribing physician. HIV testing should be performed within the study to avoid unblinding due to VISP elicited by the vaccine. Participants should refrain from HIV testing outside of the study protocol. As part of the study protocol, blood samples will be collected for ARV detection in dried blood spot and stored at pre-specified sample collection days for assessment of quantitative concentrations of tenofovir diphosphate. Additional ARV detection can be done on stored blood samples if required as per the Study Specific Procedures Binder. The use of PrEP and adherence to PrEP (if applicable) will be monitored by means of a questionnaire which will be completed by all participants approximately every 3 months.

The NIAID HIV vaccine Data and Safety Monitoring Board (further referred to as DSMB) will serve as an independent DSMB for this study and will monitor data on an ongoing basis to ensure the continuing safety of the participants and will formally monitor the efficacy endpoint.

A COVID-19 Appendix provides guidance to investigators for managing study-related procedures during the COVID-19 pandemic.

PARTICIPANT POPULATION

Screening for eligible participants will be performed within 45 days before the first administration of study vaccine or placebo at Day 1.

Study participants must be healthy (on the basis of medical history, physical examination [including vital sign measurement]), HIV-uninfected adult cis-gender men and transgender individuals having sex with cis-gender men and/or transgender individuals, aged ≥ 18 to ≤ 60 years, who are considered to be at increased risk for HIV infection. All efforts will be made to ensure that the study population includes good representation from the population at highest risk of HIV infection in terms of race, ethnicity, gender and age.

DOSAGE AND ADMINISTRATION

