8. PRESTUDY AND CONCOMITANT THERAPY

The following prestudy specific therapies administered up to 1 month before the first vaccination must be recorded at screening: analgesic/antipyretic medications and non-steroidal anti-inflammatory drugs, systemic corticosteroids, antihistaminics, mAbs, or vaccinations. Any COVID-19 vaccination must also be recorded at screening, regardless of how long before screening the vaccination took place.

The following concomitant therapies must be recorded from the first dose of study vaccine to 1 month after the last study vaccination: analgesic/antipyretic medications and non-steroidal anti-inflammatory drugs, hormonal therapy, hormone-based contraception, systemic corticosteroids, antihistaminics, mAbs, or vaccinations. Exception: Any COVID-19 vaccination

must be recorded until the end of the study. In addition, any HIV prevention medication should be recorded. The use of PrEP, PEP, hormonal therapy and hormone-based contraception should be recorded at each visit, except for the follow-up contact Visits 2a, 3a, 4a and 7a). All other concomitant therapies should also be recorded if administered in conjunction with new or worsening adverse events reported per protocol requirements outlined in Section 12.3.1. If a participant becomes HIV-1 infected during the study, use of ARVs should also be recorded.

Use of any experimental medication (including experimental vaccines other than the study vaccines) during the study is not allowed.

The use of long acting PrEP is disallowed from 24 months prior to Day 1 until after the first vaccination.

Vaccination with licensed live attenuated vaccines (for details on COVID-19 vaccines, see below) within 28 days before or after planned administration of the first or subsequent study vaccination(s) is prohibited. Other licensed vaccines (eg, tetanus, hepatitis A, hepatitis B, rabies, for details on COVID-19 vaccines, see below) should be given at least 14 days before or after administration of first or subsequent study vaccination(s) in order to avoid potential confusion of adverse reactions and potential immune interference. If a vaccine is indicated in a post-exposure setting (eg, rabies or tetanus), it must take priority over the study vaccine.

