Visit 9 to 14 are clinic visits that will include a targeted physical examination (full physical examination at Visit 14), recording of serious adverse events, MAAEs and adverse events leading to study discontinuation and HIV reduction counseling as described above for Visit 8. AESIs are to be collected up to Visit 10 (6 months after the last vaccination). Samples for HIV testing will be collected at each visit. The level of absenteeism since their last visit will be recorded. The use of PrEP, PEP, hormonal therapy, hormone-based contraception, and all COVID-19 vaccinations should be recorded at each visit. All other concomitant therapies should also be recorded if administered in conjunction with new or worsening adverse events reported per protocol requirements. Participants will complete a questionnaire on the use of and, if applicable adherence to PrEP and blood for dried blood spots will be collected for participants who have their visit on pre-specified calendar days (may differ per site).

In addition:

- If applicable, unsolicited AEs will be recorded at Visit 8
- A urine pregnancy test should be performed every 3 to 6 months
- Blood samples for syphilis serology determination will be collected and tests for chlamydia/gonorrhea will be performed at Visit 10, 12 and 14.
- Blood samples for humoral (all participants) immunogenicity assays will be collected at Visit 10, 12 and 14.

- A sexual activity questionnaire will be completed at Visit 12.
- A social impact questionnaire will be completed at Visit 14.
- Gender identity will be recorded at Visit 12.

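### SAP 5.4.2.3 decides PrEP-free status from FTC/TDF concentrations and a 30-day self-report, so users of non-tenofovir long-acting PrEP can be classed as unexposed although the trial records their use at each clinic visit

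*SAP*

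**What the plan says.** SAP 5.4.2.3 sets out two PrEP analyses, both worded as options and both conditional on substantial detected use (the example given is prevalence above 20% at some time). In the first, "a Cox model with PrEP detectability as a time-varying covariate may be used to assess different vaccine efficacy by time-varying subgroup". The second repeats the primary analysis keeping only mITT infections with no evidence of PrEP use. For the second, "FTC/TDF concentrations (see Section 3.6.1) will be used to determine eligibility for this analysis" and "A participant is eligible if their concentration is below the lower limit of detection as defined above at the diagnosis visit"; the same is required at the visit with the earliest evidence of infection, if that is a different visit. The SAP then gives a caveat, "Since the ARVs are only detectable in plasma for roughly 14 days after a single dose", and answers it with a possible extra exclusion for self-reported antiretroviral use in the last 30 days, asked about at the diagnosis visit or the visit before it.

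On data collection, Protocol 9.1.5 states for Visits 9 to 14 that "blood for dried blood spots will be collected for participants who have their visit on pre-specified calendar days (may differ per site)". The same rule stands for Visit 6 (9.1.5) and for Visits 3, 4 and 7 (9.1.4). The Protocol synopsis describes a PrEP "questionnaire which will be completed by all participants approximately every 3 months", and footnote bb of the Time and Events Schedule gives its recall period as the time since the last visit. Protocol Section 8 also has PrEP and PEP use recorded at every visit except the four reactogenicity contacts. On long-acting products Section 8 says: "The use of long acting PrEP is disallowed from 24 months prior to Day 1 until after the first vaccination".

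**The concern.** A time-varying Cox covariate needs a value for everyone at risk at each infection time. Calendar-day DBS sampling suits the prevalence tables of SAP 3.9.1.1, but it is not a per-participant series, and SAP 5.4.2.3 has no rule for a visit without an assay.

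The more serious difficulty lies in the rule the SAP does state. A concentration test for FTC/TDF says nothing about a long-acting product that contains neither drug, and the 30-day question may miss an injection given earlier in the interval. Such a participant passes both screens and enters the PrEP-free subset, while the trial holds a record that says otherwise.

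VE by and adjusted for PrEP use belongs to secondary objective 3, and Protocol 11.5.1.2 undertakes to try to estimate VE with no PrEP use at all. A PrEP-free subset containing protected people answers a different question.

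**Working it through.** **The plan's own figures.** Take 1,900 per arm, 5% excluded from PP, 10% annual dropout, 2% annual placebo incidence, VE 20% to Month 7 and 65% afterwards, with constant hazards −ln(0.90) = 0.1054 and −ln(0.98) = 0.0202 per year.
- Placebo: 1,805 × exp(−0.1256 × 7/12) = 1,677.5 at Month 7; 2,857.6 person-years over 23 months; 57.7 infections.
- Vaccine: 1,681.5 at Month 7; 2,899.2 person-years; 20.5 infections.
- Total 78.2, against 78 stated (Protocol 11.3, SAP 1.4). The figure reproduces.
- Incidence with background PrEP: 3% × (1 − 0.35 × 0.90) = 2.06%, against the 2% assumed. If 35% of person-years are on PrEP, prevalence must reach at least 35% at some time. The plan's own scenario would therefore be expected to pass the 20% example trigger, provided that use is detectable.

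**DBS coverage.** Let f be the share of eligible visits that fall on a DBS day. Neither document gives f, so it is varied over its range. The visit procedures list DBS at ten visits (3, 4, 6, 7 and 9 to 14). The 78 is used only for scale: the repeat analysis names mITT infections, for which no planned count is given. The two-visit column assumes independence and applies only where the earliest-evidence visit differs from the diagnosis visit.

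| f (assumed) | infections with DBS at one visit, 78f | at two visits, 78f² | mean DBS per participant, 10f |
|---|---|---|---|
| 5% | 3.9 | 0.2 | 0.5 |
| 10% | 7.8 | 0.8 | 1.0 |
| 20% | 15.6 | 3.1 | 2.0 |
| 50% | 39.0 | 19.5 | 5.0 |
| 75% | 58.5 | 43.9 | 7.5 |
| 100% | 78 | 78 | 10 |

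More than half the infections lack a DBS value only if f is below 50% (one visit) or below √0.5 = 71% (two visits). Below 100% the series is incomplete; by how much cannot be said.

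**What happens to an unassayed infection.** Under the sentence that keeps infections with no evidence of PrEP use, it stays in. Under the eligibility sentence, which needs a concentration below the detection limit, it does not qualify. The two sentences select different infections.

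**The 30-day look-back.** Visits 9 to 14 are planned at Days 455, 546, 637, 728, 819 and 910, so 91 days apart. If the diagnosis visit is one of these, infection lies between the last negative and first positive samples. The question at the diagnosis visit covers the last 30 of those days and leaves 91 − 30 = 61 (67%). The question at the previous visit covers 30 days before the interval opens and adds nothing within it. With windows of −14/+28 days the gap runs from 91 − 42 = 49 to 91 + 42 = 133 days, leaving 19 to 103 days unasked. The questionnaire's since-last-visit recall covers the whole interval.

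**Long-acting PrEP.** Section 8 ends its restriction after the first vaccination. The amendment summary's rationale for that restriction names cabotegravir, an injection, as its example. An FTC/TDF assay would not register it. SAP 3.9.1.1 mentions other antiretrovirals used as PrEP, but only as something the DSMB might start to monitor.

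**Cross-checks in SAP 5.4.2.3.** There is no Section 3.6.1: Section 3.6 is one sentence on the questionnaire, and DBS are in 3.9.1.1. The detection limit said to be defined earlier is not; 3.9.1.1 gives only 700 fmol/punch, as the cut-off for effective use. The caveat argues from plasma, whereas 3.9.1.1 describes DBS.

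**The case against.** The strongest reply is that the data can be obtained. The Protocol and SAP 1.2 both permit further antiretroviral testing of stored blood where needed, and SAP 5.4.2.3 does not confine the assay to DBS. With stored samples assayed at the required visits, coverage could reach every infection. The same section lets PrEP covariates draw on several data sources, and SAP 3.9.1.2 names the questionnaire and concomitant medication. Both analyses are optional.

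Much of this stands. A reader might infer that the covariate and the PrEP-free test cannot be derived for most participants or most infections. The documents do not support that: f is unstated, and stored-blood testing is available. Nor do they show that most person-time would be dropped, since the SAP is silent on unassayed visits. A reader might also take the 24 months in Section 8 as the period over which long-acting PrEP protects; it is an entry restriction, and the documents give it no other meaning.

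What the reply does not meet is the stated rule. The permission to test stored blood names no specimen, visits, participants or detection limit for this purpose. The mention of several sources concerns covariates in general, whereas eligibility for the PrEP-free repeat is tied to FTC/TDF concentrations, with self-report added only as a further optional step over 30 days.

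**Conclusion.** The concern holds as a classification rule that can go wrong when better records are already held. Users of non-tenofovir long-acting PrEP can be counted as PrEP-free. That is not certain for every such user: one who reports use within 30 days is removed if the optional exclusion is run. The documents give no uptake figure for long-acting products, so the number affected is unknown and could be zero. Incomplete DBS coverage is a second, unquantified weakness, made worse by the absence of a rule for unassayed visits.

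The effect is confined to optional secondary analyses of VE by PrEP use. The primary analysis and the 78-infection target are untouched. The conclusion assumes that the questionnaire and medication record are completed as planned. The visit procedures for Months 7 and 13 and after Month 30 do not list the questionnaire, so the medication record matters there. Versions 1.2 and 1.3 of the SAP postdate the study-level unblinding of 18 January 2023, so choices left open here would be made with results known.

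**What to change.** In SAP 5.4.2.3:

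1. Define the time-varying PrEP covariate and the PrEP-free condition from all collected sources, by the same rule for infected and uninfected participants: the since-last-visit questionnaire and the concomitant-medication record of PrEP, with any available assay as an additional source. Use the DBS sample to measure how accurate self-report is.
2. Replace the 30-day exclusion with any PrEP reported since the last HIV-negative visit. Add a labelled version in which any long-acting PrEP recorded after the first vaccination counts as exposure.
3. State that an infection without an assay is classified by these records and not dropped. Correct the reference to Section 3.6.1, name the specimen, and give its detection limit.
4. Label the change as made after unblinding.

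The cost is SAP wording and derivation programming on data already collected; stored-sample assays would be extra work and are not essential. The downside is that self-report is less accurate than an assay, which the DBS comparison can quantify. The labelled long-acting version may overstate exposure in people who stopped, which is why it should stand beside the main version and not replace it.

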- y (1) Urine sample, (2) rectal swab, and (3) oropharyngeal swab are all required. If required by standard local procedure, the collection of a urethral swab will be considered equivalent to a urine sample.
- z Venous blood samples for determination of humoral immune responses will be collected from all participants (and analyzed in a subset)
- aa Blood samples will be collected for ARV detection in dried blood spot and stored at pre specified sample collection days for assessment of quantitative concentrations of tenofovir diphosphate. Additional ARV detection can be done on stored blood samples if required, as per the Study Specific Procedures Binder.

- bb The use of PrEP at baseline and the use of PrEP and adherence to PrEP (if applicable) since their last visit will be assessed through a questionnaire. Safety monitoring for PrEP will be the responsibility of the prescribing physician.
- cc At Visit 2 (Day 1) and Visit 5 (Month 7), venous blood samples for determination of cellular immune response will be collected from participants at sites with access to sponsor approved PBMC processing facilities (and analyzed in a subset).
- dd Approximately every 6 months, blood samples for syphilis serology determination should be collected and a test for chlamydia/gonorrhea should be performed.
- ee Limited genetic testing may be performed on leftover blood from samples collected for the determination of cellular immune response. No separate blood sample is needed.
- ff Includes history and family history of immune disorders.
- gg Demographics (eg, sex assigned at birth, participant identified gender at screening, age, male circumcision, race) will be recorded at screening. Gender identity needs to be collected at Visit 7 (Month 12), Visit 12 (Month 24), approximately Month 36 and from then onwards on an annual basis.

Time and Events Schedule for Participants Who Become HIV-1 Infected

Visit # ⁱ	#.X ⁱ	Inf1	Inf2	Early Exit Inf ^b
Time in months since diagnosis ^a		M3	M6	
Visit Day		D84	D168	
Target/allowable visit window		±28d	±28d	
HIV test	●			
HIV 1 viral load measurement	●	●	●	●
CD4 ⁺ T cell count ^h	●	●	●	●
Limited genetic testing	●			
Counseling on HIV testing/diagnosis	●			
Full physical examination ^c			●	
Pregnancy test ^d		●	●	●
Targeted physical examination	●	●		●
Concomitant medication ^k		●	●	●
AE/AESI/SAE recording ^e	●	●	●	●
Transmission risk reduction counseling	●	●	●	●
Social impact questionnaire ^l		●	●	●
Absenteeism	●	●	●	●

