9.1.2. Visit Windows

The maximum screening period is 45 days, except for HIV testing which needs to be performed within 28 days prior to first vaccination.

The timings of the visits will be determined relative to the actual day of the first vaccination. For the study visits, following windows will be allowed:

- Visit 2a: (Day 9) ± 7 days[#]
- Visit 3: Month 3 (Day 84) ± 14 days
- Visit 3a: (Day 92)* ± 7 days[#]
- Visit 4: Month 6 (Day 168) -14/+28 days
- Visit 4a: (Day 176)* ± 7 days[#]
- Visit 5: Month 7 (Day 196)* -14/+28 days

- Visit 6: Month 9 (Day 273) -14/+28 days
- Visit 7: Month 12 (Day 364) -14/+42 days
- Visit 7a: (Day 372)*[±]7 days[#]
- Visit 8: Month 13 (Day 394)* -14/+28 days
- Visit 9: Month 15 (Day 455) -14/+28 days
- Visit 10: Month 18 (Day 546) -14/+28 days
- Visit 11: Month 21 (Day 637) -14/+28 days
- Visit 12: Month 24 (Day 728) -14/+28 days
- Visit 13: Month 27 (Day 819) -14/+28 days
- Visit 14: Month 30 (Day 910) -14/+28 days

* If a participant is not vaccinated on the given day of vaccination, ie, Visit 3 (Day 84), Visit 4 (Day 168) and Visit 7 (Day 364), the timings of the study site Visits 5 and 8 and follow-up contact Visits 3a, 4a and 7a, will be scheduled relative to the actual day of vaccination.

The site staff and the participant will make multiple efforts in good faith to be in contact after the last day of the reactogenicity period, or sooner if indicated, to discuss presence of any signs and symptoms of reactogenicity. Participants who self-report any post-vaccination reaction greater than mild are seen by a clinician within 48 hours after onset, unless the reaction is improving and/or has resolved completely.

Every effort should be made to follow the vaccination schedule per the protocol. Vaccinations should generally not be administered outside the prespecified window. If a participant cannot be vaccinated within the predefined window, the HPX3002/HVTN 706 safety review team can determine on a case-by-case basis if the participant can still be vaccinated. Note that cases of out of window vaccination due to per protocol allowed COVID-19 vaccination (see Section 8) should be notified to the sponsor and do not need safety review team approval. There should be a time interval of at least 28 days between study vaccinations.

The allowed time window for the follow-up visits scheduled every 3 months post Month 30 is \pm 28 days. Visits post Month 30 will be scheduled relative to the Month 30 visit.

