9.2. Efficacy Evaluations

An HIV test will be performed approximately every 3 months (see [Time and Events schedule](#)). To avoid delays in initiation of combined antiretroviral treatment, local HIV PCR testing is allowed only in case of suspected acute HIV infection, in case of recent HIV exposure, or in case a request for sample redraw is received from the central HIV testing laboratory for confirmation of an HIV positive test. Upon discretion of the investigator, additional HIV tests may be performed during unscheduled visits; participants should refrain from performing any HIV testing outside of the study protocol. Testing will be performed according to a sponsor-approved HIV-1-testing algorithm that differentiates VISp (see below) from true HIV-1 infection. An endpoint adjudication process will be in place to assess all serological and virological testing, in a blinded

manner, on each participant in the study who, prior to study unblinding, tests positive per the sponsor-approved HIV testing.

If a participant has a confirmed positive HIV test during the study, the participant will remain in the study but no further scheduled vaccinations will be administered. The study staff will receive a report confirming the diagnosis. Confirmed HIV-1 infection should not be recorded as (serious) adverse event. The participants will be provided counseling, will be referred for medical treatment and, if applicable, will be informed about observational studies monitoring participants with HIV infection. Further assessments, including HIV-1 viral load measurements, CD4⁺ T cell count, and viral sequencing (samples taken in all participants and analyzed to assess whether VE differs by genotypic characteristics of HIV and whether there is evidence of vaccine-induced immune pressure on the viral genotype, depending on the vaccine efficacy outcome) will then be performed according to the [Time and Events Schedule for Participants Who Become HIV-1 Infected](#).

VISP

In general, HIV-uninfected participants in preventative HIV-vaccine studies may develop HIV-specific antibodies as a result of an immune response to the candidate HIV-1 vaccine, referred to as VISp (also known as VISr). These antibodies may be detected in common HIV-serologic tests, causing the test to appear positive even in the absence of actual HIV infection. Vaccine-induced seropositivity may become evident during the study or after the study has been completed.

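### The 30-day self-report exclusion in SAP 5.4.2.3 leaves about two thirds of a standard infection interval unchecked for PrEP, although the trial already records PrEP use over the whole interval

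*SAP*

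**What the plan says.** SAP 5.4.2.3 applies if PrEP use is substantial (prevalence above 20% is the example given). The efficacy analysis may then be repeated with only those mITT infections that show no sign of PrEP at diagnosis or at the earliest evidence of infection. The screen is a drug level: "FTC/TDF concentrations (see Section 3.6.1) will be used to determine eligibility for this analysis". The SAP gives the weakness of this screen itself: "Since the ARVs are only detectable in plasma for roughly 14 days after a single dose", an infection may predate that window, so absence of prophylaxis at infection is not assured. As the answer, a further analysis may also exclude participants "if they self-report ARV use in the last 30 days at either the diagnosis visit or the last visit prior to diagnosis".

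The protocol supplies the timing and the available data:

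- Section 9.2: "An HIV test will be performed approximately every 3 months".
- Section 9.1.2: for example "Visit 9: Month 15 (Day 455) -14/+28 days" and "Visit 10: Month 18 (Day 546) -14/+28 days".
- Time and Events Schedule, footnote bb: "the use of PrEP and adherence to PrEP (if applicable) since their last visit will be assessed through a questionnaire".
- Section 8: PrEP and PEP are recorded at every visit except the four post-vaccination contacts. On long-acting agents: "The use of long acting PrEP is disallowed from 24 months prior to Day 1 until after the first vaccination".

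SAP 3.9.1.2 already summarizes both the questionnaire and the concomitant medication record.

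**The concern.** The second exclusion exists to repair a look-back that is too short, but its own look-back is also short relative to the testing interval. An infection first detected at one visit was acquired at some point since the last negative sample, usually about three months earlier. A 30-day recall at the diagnosis visit reaches back over one third of that time. The same recall at the visit before looks at time before the interval opened.

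The drug-level rule does not fill the gap. It names FTC/TDF, while PrEP of any kind is allowed after the first vaccination. Dried blood spots are taken only at visits that fall on pre-specified calendar days (Protocol 9.1.4 and 9.1.5).

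What is at stake is the meaning of an estimate presented as efficacy against infections acquired off PrEP. If some retained cases were on PrEP, the estimate mixes the two groups. That matters if efficacy differs by PrEP use or if uptake differs by arm. If neither differs, the ratio is unaffected, but the analysis still does not give the assurance it was added to give.

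**Working it through.** The plan states no coverage figure, so there is nothing to reproduce first. The check is interval arithmetic.

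**Inputs.** Self-report look-back of 30 days (SAP 5.4.2.3). Scheduled days 196, 273, 364, 394, 455, 546, 637, 728, 819 and 910 for Months 7, 9, 12, 13, 15, 18, 21, 24, 27 and 30 (Protocol 9.1.2). The Month 13 sample is tested only when Month 15 is positive and Month 12 negative (Time and Events Schedule, footnote k).

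**Formula.** Uncovered share = max(0, gap − 30) / gap, where gap is the number of days between the last negative and first positive samples. The 30 days before the prior visit lie before the gap opens and add nothing to it.

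| Interval | Gap (days) | Uncovered (days) | Share |
|---|---|---|---|
| M9–M12, and each gap from M15 to M30 | 91 | 61 | 67% |
| M7–M9 | 77 | 47 | 61% |
| M12–M13 | 30 | 0 | 0% |
| M13–M15 | 61 | 31 | 51% |

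**Average over Month 7 to Month 30 (910 − 196 = 714 days).**
- With the Month 13 sample: 47 + 61 + 0 + 31 + 5 × 61 = 444; 444/714 = 62%.
- Without it: 47 + 7 × 61 = 474; 474/714 = 66%.

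**Visit windows.** For two visits scheduled 91 days apart, both with the −14/+28 window:
- Shortest gap: 91 − 28 − 14 = 49 days; (49 − 30)/49 = 39%.
- Longest gap: 91 + 14 + 28 = 133 days; (133 − 30)/133 = 77%.

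**Delay before infection is detectable (assumed 0 to 30 days; not in the documents).** The interval at risk moves back by the delay. Days lost from the diagnosis-visit report are gained from the prior-visit report, so coverage stays at 30 of 91 days and the 67% does not change.

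**Drug level alone.** (91 − 14)/91 = 85% uncovered. The 14 days is a single-dose plasma figure, whereas the assay described in SAP 3.9.1.1 uses dried blood spots, so I place no weight on this number.

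**Which use escapes.** On the 91-day schedule the two reports cover days 0–30 and days 91–121 before diagnosis (91 + 30 = 121). Use confined to days 31–91 escapes both. For a long-acting injection, which the FTC/TDF rule does not look for, so does one given more than 121 days before diagnosis.

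**With the since-last-visit record.** Self-report spans 91 of 91 days, so the uncovered share of a standard interval falls from 67% to 0%, subject to recall accuracy and missed visits.

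**The case against.** The strongest reply is that uncovered days are not missed cases. Someone on continuing PrEP reports it at diagnosis, at the visit before, or at both, and is excluded. Only use confined to the gap escapes, and nothing in the documents says how common that is. This stands. A reader might infer that two thirds of PrEP-exposed infections are misclassified, or might use the design assumption of about 35% of person-years on PrEP to put a number on them. Neither inference is supported.

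A reader might also infer that long-acting PrEP is missed altogether. It is not: the self-report exclusion covers any ARV, so an injection within 30 days of either visit is caught. SAP 3.9.1.1 and the protocol also allow assays for other antiretrovirals, but these are optional and are not part of the eligibility rule in 5.4.2.3.

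Nor is this the only PrEP analysis. SAP 5.4.2.3 also has subgroup and covariate analyses using the different PrEP data sources and a Cox model with time-varying detectability. Protocol 11.5.1.2 mentions a counterfactual approach.

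The analysis is conditional and then optional, it leaves the primary result untouched, and the SAP is candid about the drug-level step. All of that limits the importance of the point. It does not answer it, because the SAP presents the 30-day step as the remedy.

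Finally, the prior-visit report has a use: where the visit before diagnosis turns out to hold the earliest evidence of infection, it is the relevant report. That is a reason not to drop it outright.

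**Conclusion.** The point holds in a limited form. The 30-day exclusion does not do what SAP 5.4.2.3 says it does. It leaves 67% of a standard 91-day interval unchecked, 62% to 66% averaged over Month 7 to Month 30, and 39% to 77% across the visit windows for a 91-day interval. The gap is about half for Month 13 to Month 15 and nil for Month 12 to Month 13. These figures assume that visits are attended and that infection falls between the last negative and first positive samples; they do not change for a detection delay of up to 30 days.

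The number of misclassified infections cannot be derived from the documents, and no bias in the efficacy estimate is shown. The case for changing the rule is that a better measure of the same exposure is already collected. This is worth correcting, but it concerns one optional secondary analysis.

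**What to change.** In SAP 5.4.2.3, replace the 30-day rule for this analysis:

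- Class an infection as PrEP/PEP-exposed if the since-last-visit questionnaire or the concomitant medication record shows any PrEP or PEP, of any agent, between the last negative and first positive sample dates, or if ARV is detected at the tested visits.
- Keep the prior-visit report where that visit is the one with the earliest evidence of infection.
- Count any recorded long-acting injection using a look-back stated in the SAP. The protocol's 24-month restriction governs the period before Day 1 and need not set its length.
- Correct the cross-reference to Section 3.6.1, which does not exist in the current SAP (dried blood spots are in 3.9.1.1), and define the detection limit on which the rule relies.
- Date the change and label it as made after study-level unblinding on 18 January 2023.

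The cost is SAP wording and a revised derivation from data already collected. Some further cases will be removed, how many is not known from the documents, and the interval for this optional analysis will be wider. The primary analysis does not change.
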